3.7 Interim Analysis

An interim analysis will be conducted by an independent unblinded statistician and reviewed by the independent DSMB. This analysis will be based on primary efficacy endpoint data for the first approximately 60 participants randomized in the BK ITT Population. The interim analysis will be performed for the purpose of potentially stopping early for futility. If the study is not

stopped based on the interim analysis, then accrual to the study will continue until there are 105 participants in the BK ITT Population.

The interim analysis for stopping early for futility will be based on the primary efficacy endpoint. The decision to stop for futility is based on the conditional probability that the study will be successful, assuming the current trend observed at the interim, should it continue to the sample size of 105 participants in the BK ITT Population with participants being followed for 24 weeks. The calculation will assume that the final analysis will be a log-rank test with overall alpha = 0.025 (one-sided) adjusted for the interim analysis. If, at the interim analysis, the conditional probability of study success with 105 BK ITT Population participants falls below 5%, the study will stop early for futility (Lachin 2005). Enrollment and participant follow-up will then be discontinued, and the final analyses will be conducted. The futility stopping in this study is considered non-binding.

REFERENCE

Lachin JM. (2005). A review of methods for futility stopping based on conditional power. Stat Med 2005;24 (18):2747-64).

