2.2 Secondary Objectives

The key secondary objective is to compare the time to resolution of bladder pain as measured by Clinical Outcome Assessments (COAs) in recipients of PSL to that in recipients of placebo.

Other secondary objectives include comparisons of the following in recipients of PSL and recipients of placebo:

- To assess number of days in the hospital (for any reason including HC) over the 24-week study period.
- To assess the incidence and severity of acute GVHD and cytokine release syndrome (CRS) over the 24-week study period.
- To assess time to resolution of viremia for all target viruses over the 24-week study period (only for participants with detectable viremia at baseline).
- To assess average daily bladder pain (11-point numeric rating scale [NRS]) over the 6-week period from randomization.

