9.2.2 Analysis of Safety

The safety profile will be based on treatment-emergent adverse events (TEAEs) and changes in vital signs, physical examinations, clinical laboratory assessments, and ECGs. All safety analyses will be based on the Safety Population.

Safety analyses in general will be descriptive and will be presented by phase and treatment group in tabular format. Categorical endpoints will be summarized using the number and percentage of participants within each category. Continuous endpoints will be summarized descriptively with summary statistics (number, mean, standard deviation, standard error, median, first quartile, third quartile, minimum, and maximum).

A TEAE is defined as an adverse event with onset after the start of study treatment (PSL or placebo). The number and percentage of participants with TEAEs will be tabulated by MedDRA System Organ Class and Preferred Term for each treatment group and by severity and relationship to treatment. Adverse events leading to discontinuation of the study and SAEs will be summarized by treatment group. By-participant listings will also be provided for any deaths, SAEs, and adverse events leading to discontinuation of the study.

The key safety endpoint for this study is the incidence and severity of acute GVHD. The incidence and severity of acute GVHD, chronic GVHD, and CRS, and the corresponding exact binomial confidence intervals with 95% confidence level will be presented by treatment group.

Descriptive statistics will be provided for clinical laboratory data, vital sign data, and ECG parameters, presented as both actual values and changes from baseline over time. Abnormal physical examination findings will be presented in a by-participant data listing.

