9.2.3.2 Interim Analysis for Futility

The interim analysis for futility will also be based on the primary efficacy endpoint. The decision to stop for futility is based on the conditional probability that the study will be successful should it continue to the sample size of 105 participants in the BK ITT Population with participants being followed for 24 weeks. The calculation will assume that the final analysis will be a log-rank test

conducted at the one-sided 0.0147 level. If, at the interim analysis, the conditional probability of study success with 105 BK ITT Population participants falls below 5%, the study will stop early for futility. Enrollment and participant follow-up will then be discontinued, and the final analyses will be conducted. The futility stopping in this study is considered non-binding.

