2.1.2 Secondary Objectives

The key secondary objective is to compare the time to resolution of bladder pain as measured by clinical outcome assessments (COAs) in recipients of PSL to that in recipients of placebo.

Other secondary objectives include comparisons of the following in recipients of PSL and recipients of placebo:

- To assess number of days in the hospital (for any reason including hemorrhagic cystitis [HC]) over the 24-week study period.
- To assess the incidence of acute graft versus host disease (GVHD) and cytokine release syndrome (CRS) over the 24-week study period.
- To assess time to resolution of viremia for each target virus over the 24-week study period (only for participants with detectable viremia at randomization).
- To assess average daily bladder pain over the 24-week study period.
- To assess time to global impression of hemorrhagic cystitis severity of none or mild.

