Safety assessments including, but not limited to chemistries, complete blood counts with differentials, and physical examinations will be performed. Adverse events will be assessed.

As GVHD is a theoretical safety concern, the incidence and severity of GVHD will be monitored during the study. No participants will be permitted to receive a second infusion of PSL or placebo if they develop worsening of GVHD at the proposed time of infusion of the second dose.

Analgesic use will be collected by the study staff and a pain medication log within the electronic patient-reported outcome (ePRO) system will be completed by outpatients.

Participants will be followed on the study for 24 weeks after the participant's first infusion with study treatment.

An independent Data and Safety Monitoring Board will be convened for this study to routinely monitor participant safety and evaluate a prespecified interim analysis for the purpose of potentially stopping the study early for futility.

A summary of the study design is shown in Figure 1.

Figure 1. Summary of Study Design

R = Randomization (on Day 1)

See section 3.1.1 (Analysis Day) for an explanation of the differences in definitions of day of the first dose and randomization between the SAP and the protocol.

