3.5.2 AEs of Special Interest

The AESIs will be reviewed by the DSMB as per the DSMB Charter. Criteria for acute and chronic GVHD and CRS can be found in Protocol Appendices E, F and G. The number and percentage of participants who had the treatment-emergent AESIs will be summarized by treatment group:

- Severity and incidence of acute GVHD
- Severity and incidence of chronic GVHD
- Severity and incidence of CRS
- Severity and incidence of infusion-related AEs
- Severity and incidence of graft failure and rejection

For GVHD, a separate table will be prepared that summarizes:

- aGVHD by MAGIC overall grade and by stage and organ involvement
- cGVHD by NIH score

Subgroup analyses may be conducted for the severity and incidence of acute GVHD by HLA Class (I, II, and I & II) and the number of HLA matches.

Incidence and severity of AESI and the corresponding exact binomial confidence intervals with 95% confidence level will be presented by treatment group.

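### A futility stop ends follow-up of already infused participants, so 24-week GVHD and CRS incidence would be incomplete and understated

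*SAP*

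**What the plan says.** The futility rule uses conditional power for the primary endpoint, resolution of macroscopic hematuria. If it falls below 5%, SAP 3.7 says "Enrollment and participant follow-up will then be discontinued, and the final analyses will be conducted". Protocol 9.2.3.2 has the same sentence and adds the status of the rule: "Enrollment and participant follow-up will then be discontinued, and the final analyses will be conducted. The futility stopping in this study is considered non-binding". Neither section exempts safety follow-up.

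Elsewhere the documents set a 24-week horizon:

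- SAP 2.2.1: "Participants will be followed on the study for 24 weeks", counted from the first infusion. Protocol 3.1 says the same.
- Protocol 2.2: "To assess the incidence and severity of acute GVHD and cytokine release syndrome (CRS) over the 24-week study period". SAP 2.1.2 keeps the horizon: "To assess the incidence of acute graft versus host disease (GVHD) and cytokine release syndrome (CRS) over the 24-week study period".
- Protocol 9.2.2: "The key safety endpoint for this study is the incidence and severity of acute GVHD".
- SAP 3.5.2, on the analysis: "Incidence and severity of AESI and the corresponding exact binomial confidence intervals with 95% confidence level will be presented by treatment group". No time-at-risk method is named.

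The documents also provide a partial safety net. Termination by the sponsor is a listed reason for leaving the study. It triggers an effort to obtain an Early Termination Visit with the Week 24 assessments (Protocol 4.3.1). Serious adverse events are followed to outcome (8.3.2), and those judged related stay reportable after participation ends (8.3.1).

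**The concern.** Futility is a judgment about hematuria. It says nothing about GVHD, CRS or graft failure, which the protocol lists as adverse events of special interest (8.1.4). Protocol 1.5.1 names GVHD among the main risks. After a futility stop, the safety record of third-party T cells is the main lasting result of the trial, and that is when the plan cuts it short.

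The safety net does not fill the gap. For someone infused three weeks earlier, an Early Termination Visit measures three-week risk. Adverse event collection ends with participation (Protocol 8.1), so new non-serious GVHD after that visit would not be captured. After baseline, chronic GVHD is evaluated only at the last two visits in Appendix A, Weeks 12 and 24, and the most recently infused would miss both as scheduled.

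The analysis then turns lost time into bias. A participant seen for three weeks without GVHD enters the binomial denominator exactly like one seen for 24. Protocol 4.3.2 takes the opposite attitude to participants barred from further infusions: it asks for every effort to keep them in follow-up.

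**Working it through.** **Inputs.** About 125 randomized to give 105 BK ITT, with an 85% BK share (Protocol 9.2.4, SAP 2.2.3); enrollment about 15 months (Protocol 3.1); interim on about the first 60 BK ITT participants (SAP 3.7). The required follow-up of those 60 is not stated. Assumed here: uniform accrual, randomization as proxy for first infusion, and no dropout.

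**The plan's own figures.**

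- 105 / 0.85 = 123.5, consistent with about 125.
- Power at 20% dropout, with medians of 6 and 12 weeks: event probabilities are 0.879 (PSL) and 0.689 (placebo). The allocation ratio is blacked out. At 1:1 there are 82.3 events and the power is 88.2%; at 2:1, 85.7 events and 85.6%. The stated 86.4% lies between.

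**How many are truncated.**

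- Rate: 125 / 15 = 8.33 per month.
- 24 weeks = 168 / 30.44 = 5.52 months.
- Inside the 24-week window at any time: 8.33 × 5.52 = 46.
- Randomized when the 60th BK ITT participant enters: 60 / 0.85 = 70.6, about 71. Each further 12 weeks adds 8.33 × 2.76 = 23.

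Truncated participants have on average 12 of their 24 weeks, so 46 × 12 = 552 person-weeks are lost.

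| Interim run | Randomized | Full 24 weeks possible | Truncated | Person-time lost |
|---|---|---|---|---|
| At 60th entry | 71 | 25 | 46 (65%) | 552 / (71 × 24) = 32% |
| 12 weeks later | 94 | 48 | 46 (49%) | 552 / (94 × 24) = 24% |
| 60th completes 24 weeks | 117 | 71 | 46 (39%) | 552 / (117 × 24) = 20% |

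At an assumed 30 months, 125 / 30 × 5.52 = 23 are truncated: 33%, 28% and 25% of about 71, 82 and 94. At an assumed 12 months and the earliest timing it is 57, or 81%.

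**Size of the understatement.** The documents give no GVHD rate or onset times, so this is only an illustration.

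- If onset is even over 24 weeks, truncated participants show half of their events. The crude incidence is then (25 + 46 × 0.5) / 71 = 68% of the 24-week value at the earliest timing, and (71 + 46 × 0.5) / 117 = 80% at the latest.
- If all onset falls evenly in the first 12 weeks, truncated participants show 0.5 + 0.5 × 0.5 = 75% of events. The figures become (25 + 34.5) / 71 = 84% and (71 + 34.5) / 117 = 90%.

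**How likely is the scenario.** Take t = 60/105 = 0.571, assuming information proportional to participants. Conditional power under the current trend is below 5% when z < √t × (1.96 − 1.645 × √(1 − t)) = 0.756 × (1.96 − 1.077) = 0.67. With no treatment effect the probability is about 75%; under the design effect it is 4% to 5%.

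**The case against.** The strongest case on the other side is that this is a rule with a stated exception. The 24-week statements describe the normal course, and Protocol 4.3.1 and section 5 expressly allow the study to end early. The rule is non-binding, and the DSMB charter, not among these documents, may say more. That is fair against calling the passages contradictory. It does not remove the problem: non-binding status governs whether to stop, and the text is explicit about what follows a stop.

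A reader might go further and infer any of three things that the documents do not support.

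- *The 24-week objective could not be answered.* About 25 to 71 participants could already have full data on the 15-month plan, and the Early Termination Visit includes both GVHD evaluations.
- *Follow-up ends on the day of the decision.* No timetable is given, and an orderly close-out fits the wording.
- *Two-thirds of participants are cut off.* The 65% is the earliest timing only, and an interim resting on primary endpoint data would probably come later. Accrual may also have been slower than 15 months: protocol v5.0 is dated February 2022, and the SAP of November 2023 still places the interim ahead. The enrollment start date is not given, so this is inference.

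Three further points stand. Acute GVHD evaluations are front-loaded (Weeks 1, 2, 4, 6, 12 and 24), and Appendix G centers CRS vigilance on the first four weeks, so CRS suffers little except in very recent infusions. Chronic GVHD is exploratory. And the crude binomial method ignores dropout and death even in a completed trial, so continuing follow-up alone would not cure it.

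**Conclusion.** The concern holds as a poor consequence of an explicit rule in both documents. On a futility stop, everyone still within 24 weeks of first infusion loses scheduled safety follow-up. The 24-week acute GVHD and CRS objective is then answered incompletely, and the planned incidences understate 24-week risk. On the 15-month plan about 46 participants are affected, 39% to 65% of those randomized depending on when the interim is run; at an assumed 30 months, about 23. These counts rest on uniform accrual and no dropout; with dropout, fewer would still be in follow-up to lose. The direction of the bias is clear, but its size depends on GVHD onset times that the documents do not give. Randomization should make truncation similar in the two arms, so the main damage is to the absolute 24-week risk rather than to the ratio between arms.

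**What to change.** Change the sentence in both Protocol 9.2.3.2 and SAP 3.7. Suggested text: *Enrollment will then be discontinued. Participants who have received any study treatment will complete the scheduled safety follow-up (adverse events, AESI, acute and chronic GVHD) through Week 24. The final safety analysis will be conducted when the last dosed participant completes Week 24 or discontinues. The efficacy analysis may be conducted at the time of the stop.*

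Then:

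- Reconcile the new text with the 24-week follow-up statements in Protocol 3.1 and SAP 2.2.1.
- Make clear under SAP 3.1.9, which sends data collected after the end of study to listings only, that these data enter the summary tables.
- In SAP 3.5.2, add beside the binomial incidence a cumulative-incidence analysis of GVHD with death as a competing event, or an exposure-adjusted analysis. This helps whether or not the study stops.

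On the 15-month plan, potential 24-week coverage before dropout rises from about 25 of 71 to 71 of 71 at the earliest interim timing, or from about 71 of 117 to 117 of 117 at the latest. The cost is an amendment to both documents, up to 24 more weeks of visits already in the schedule, and later final safety tables. The documents contain no budget, so the expense cannot be judged here. N, alpha and the stated power do not change.

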9.2.1 Analysis of Efficacy

9.2.1.1 Primary Efficacy Endpoint Analysis

The primary endpoint is the time to resolution of macroscopic hematuria in participants with documented BK viruria. Resolution of macroscopic hematuria is defined as resolution to Grade 0 or 1 on the Bedi scale⁴⁷ on 2 consecutive urine assessments \geq 2 days apart without continuous bladder irrigation or nephrostomy tubes; Grade 1 requires confirmation of resolution by urinalysis results of \leq 100 RBCs/HPF. If a participant has nephrostomy tubes that are capped, Bedi assessments may be performed, including for the purpose of assessing for resolution.

The objective is to demonstrate the superiority of PSL therapy to placebo with respect to the time to resolution of macroscopic hematuria.

The primary efficacy analysis will be conducted after all participants have completed 24 weeks of follow up or discontinued from the study. At the primary analysis, the PSL group will be compared to the placebo group in the BK ITT Population using a stratified log-rank test based on the stratification factors at randomization. The study will be considered a success if the one-sided p-value from the stratified log-rank test comparing treatment to control is less than 0.0147 (reduced from 0.025 due to inclusion of an interim analysis based on Pocock method). A supplementary efficacy analysis based on the overall ITT Population will also be conducted. Time to resolution will be calculated from the time of randomization to the date of the first resolution of macroscopic hematuria (see Section 7.1). Participants not observed to achieve resolution will be considered censored at their last follow-up for the primary endpoint. Definitive therapies to stop bladder bleeding, such as cystectomy, bladder vessel embolization, cauterization, application of fibrin "glue" preparations, or formalin instillation are permitted but will be considered treatment failures for the primary endpoint of time to resolution of macroscopic hematuria and will be censored at 24 weeks. The detailed censoring rules will be specified in the SAP.

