3.4 Efficacy Analyses

3.4.1 Primary Efficacy Endpoint

The primary endpoint is the time to resolution of macroscopic hematuria in participants with documented BK viruria. Resolution of macroscopic hematuria is defined as resolution to Grade 0 or 1 on the Bedi scale on 2 consecutive urine assessments \geq 2 days apart without continuous bladder irrigation or nephrostomy tubes that are uncapped; Grade 1 requires confirmation of resolution by urinalysis results of \leq 100 RBCs/HPF. If a participant has nephrostomy tubes that are capped, Bedi assessments may be performed on urine voided through the urethra or a bladder catheter (eg, Foley or suprapubic catheter), including for the purpose of assessing for resolution.

If the Bedi grade at randomization is missing, then the most recent screening Bedi grade will be used if available. If there are no Bedi grades at either randomization or during screening, the participant will be assumed to be eligible. The primary efficacy analysis will be conducted after all participants have completed 24 weeks of follow up or discontinued from the study. At the primary analysis, the PSL group will be compared to the placebo group in the BK ITT Population using a stratified log-rank test adjusting for stratification factors at randomization (derived based on EDC data). The study will be considered a success if the one-sided p-value from the stratified log rank test comparing treatment to control is less than 0.025. A stratified Cox proportional hazards model will be conducted to produce the hazard ratio of the treatment effect.

Time to resolution will be calculated starting from the date of randomization to the date of the first visual urine assessment without macroscopic hematuria (by the Hemostick® visual scale with score of 0 for outpatients; by the Bedi scale with a Grade 0 or 1 for inpatients) will be used, but 2 consecutive Bedi grades of 0 or 1 are required to establish resolution as noted above. If an outpatient does not have a Hemostick score at the time of resolution, the first of the 2 consecutive Bedi grades of 0 or 1 will be used for determining the time to resolution, which is the same approach being applied to inpatients. For inpatients who resolve on the date of hospital discharge, the Bedi grade scored on the discharge date will be used for determining time to resolution if available; if no Bedi grade is available at the time of discharge, then the Hemostick score will be used.

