Participants not observed to achieve resolution will be considered censored at their last study follow up. Definitive therapies to stop bladder bleeding, such as cystectomy, bladder vessel embolization, cauterization, fulguration, or formalin instillation are permitted. If it is given before or on the day of randomization, the participant will be included in the BK ITT analysis assuming a Bedi of 2 or above. If it is given post randomization, it will be considered treatment failure for the primary endpoint of time to resolution of macroscopic hematuria and will be censored at the last follow-up time of any participant. Participants who discontinued early from the study before

achieving resolution will be censored at the time of last follow up. Participants who died or took non-PSL VSTs prior to reaching resolution will be considered treatment failures and censored at the last follow-up time of any participant.

For Bedi assessments where the grade is not evaluable and the participant is receiving continuous bladder irrigation, has nephrostomy tubes that are uncapped, or the urine is visually bloody, macroscopic hematuria is considered unresolved. For all other Bedi assessments where the grade is not evaluable, the grade is considered missing.

The analysis date for a Bedi assessment is the visual assessment date. If there is no visual assessment date, the urine collection date will be used. Otherwise, the visit date will be used. One Bedi assessment will be selected per analysis date. If there are multiple Bedi assessments on the same analysis date, the worst case is selected. If for a visit, there are Bedi assessments with a visual assessment date or urine collection date, assessments with only a visit date will not be selected.

If there are multiple Hemostick scores on the same date, the highest score will be selected.

If the result of the primary efficacy endpoint (ie, time to resolution of macroscopic hematuria) is statistically significant based on the BK ITT Population, a formal hypothesis test will be conducted sequentially of this same endpoint based on the overall ITT Population using a one-sided 0.025 significance level.

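### After a futility stop, treatment failures stay at risk longer than they could have been observed, so the reported resolution rates come out slightly too low

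*SAP*

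**What the plan says.** **Failure rule.** Under SAP 3.4.1, participants who die or take non-PSL VSTs before resolution "will be considered treatment failures and censored at the last follow-up time of any participant". Definitive therapy given after randomization is handled in the same way: it "will be censored at the last follow-up time of any participant". The estimand table in that section repeats this for all three events. Protocol 9.2.1.1 instead gives a fixed time, for definitive therapy only: "and will be censored at 24 weeks".

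**Planned timing.** SAP 3.4.1: "The primary efficacy analysis will be conducted after all participants have completed 24 weeks of follow up or discontinued from the study".

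**Interim.** SAP 3.7: "This analysis will be based on primary efficacy endpoint data for the first approximately 60 participants randomized in the BK ITT Population". The section gives no data cutoff, no minimum follow-up and no separate censoring rule. Futility is judged by conditional power "assuming the current trend observed at the interim", against a 5% threshold, and the rule is non-binding.

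**After a futility stop.** SAP 3.7: "Enrollment and participant follow-up will then be discontinued, and the final analyses will be conducted". Protocol 9.2.3.2 provides for the same. Neither document modifies the failure rule for this case.

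**The concern.** Keeping a failure in the risk set as a participant who can no longer resolve is a recognized device. It makes the Kaplan-Meier curve approximate the cumulative incidence of resolution, provided everyone has the same potential follow-up.

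With staggered follow-up the device breaks down. Take two participants randomized three weeks before the cutoff. One is alive and unresolved, and leaves the risk set at Week 3. The other died at Week 2, and stays in it to about Week 24. Failures therefore accumulate in the late risk sets, the estimated late resolution hazard is too small, and resolution is understated. This is bias, so it does not shrink with sample size.

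At stake are the resolution estimates reported after a futility stop and, if the interim data are immature, the inputs to the 5% futility decision.

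**Working it through.** **1. Reproduce the plan's power (SAP 2.2.3).** Inputs: medians 12 and 6 weeks, exponential; 24 weeks of follow-up; 20% dropout; 105 participants; one-sided 0.025. The allocation ratio is not visible, so 1:1 and 2:1 were both tried.

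- Resolution hazard λ = ln2/median: 0.0578 per week (placebo), 0.1155 (PSL). Dropout hazard c = −ln(0.8)/24 = 0.0093.
- P(event) = λ/(λ+c) × [1 − exp(−24(λ+c))]: placebo 0.861 × 0.80 = 0.689; PSL 0.925 × 0.95 = 0.879.
- 1:1: 52.5 × (0.689 + 0.879) = 82.3 events, Schoenfeld power 88.2%. 2:1: 85.7 events, 85.6%. The stated figure is 86.4%, so both agree within 2 points.
- Simulated log-rank with the futility stop: 87.0% (1:1) and 80.7% (2:1).

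**2. How unequal is follow-up after a futility stop?** Protocol 3.1 gives an enrollment period of about 15 months, or 65 weeks. Assume uniform accrual.

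- Rate: 105/65 = 1.615 BK ITT participants per week.
- 60th randomized at 60/1.615 = 37.1 weeks. That participant reaches 24 weeks at 61.1.
- Randomized by then: 61.1 × 1.615 ≈ 98. Nothing in the documents pauses accrual.
- Randomized in the last 24 weeks: 24 × 1.615 = 38.8, and 38.8/98.8 = 39%.

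The wait in SAP 3.4.1 does not help here. Once follow-up is discontinued, these participants count as having discontinued.

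**3. Rules compared.** (A) SAP: failures censored at the maximum follow-up of any participant. (B) Failures censored at their own potential follow-up, min(24 weeks, cutoff − randomization). The true value is the cumulative incidence λ/(λ+h) × [1 − exp(−24(λ+h))], with h = −ln(1−q)/24 for an assumed failure proportion q by 24 weeks. For q = 20% it is 68.9% (placebo) and 87.9% (PSL).

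**4. Week-24 resolution** (1:1, 15-month accrual, 20% dropout, q = 10-30%, large-sample runs):

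| Data cut | A below B, per arm |
|---|---|
| 24 weeks after the 60th, all randomized included | 0.7-1.6 points |
| 12 weeks after the 60th | 0.9-2.1 points |
| At the 60th randomization | 1.6-3.2 points |

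Rule B was closer to the truth in every case. At q = 20% (placebo/PSL):

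- Cut at the 60th: A 65.6%/84.6%, B 68.3%/86.9%, truth 68.9%/87.9%.
- Stop 8 weeks after the 60th, recent enrollees included: A 66.2%/85.5%, B 68.2%/87.4%; log HR 0.672 (A) and 0.685 (B).

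**5. Current-trend conditional power (CP), if the interim is cut at the 60th randomization** (1:1; 2,000-4,000 trials per scenario):

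| Scenario (failures placebo/PSL) | Mean CP, A | Mean CP, B | P(CP<5%), A vs B |
|---|---|---|---|
| Design effect, 20%/20% | 0.707 | 0.717 | 8.1% vs 7.7% |
| Design effect, 15%/30% | 0.604 | 0.634 | 14.2% vs 12.6% |
| Design effect, 25%/15% | 0.751 | 0.750 | 5.1% vs 5.5% |
| Design effect, 30%/15% | 0.781 | 0.778 | not reported |
| No effect, equal failures | 0.147 | 0.148 | not reported |

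With no effect and unequal failures, mean CP shifts by −1.0 or +1.3 points. The futility call differs between the rules in 0.4% to 5.6% of trials. At q = 20% with the cut 12 weeks later, mean CP is 0.717 (A) and 0.721 (B). With 24 weeks for all 60, the rules are identical.

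**The case against.** - **Interim maturity is not stated.** SAP 3.7 may intend complete data on the first 60, and the DSMB charter may say so. This stands for the interim. It does not answer the futility-stop case, where SAP 3.7 itself creates unequal follow-up however mature the 60 are.
- **Conditional power.** A reader might infer that the rule biases the trial towards futility. The simulations do not support that: the shift is small, its sign varies, and it is essentially nil under no effect with equal failure rates.
- **Error rate and primary result.** A reader might also infer inflated type I error or a compromised primary analysis. Neither follows. Futility is non-binding, the SAP has no efficacy stop, and the planned analysis waits for full follow-up.
- **Size.** Gaps of 4 to 5 points can be produced with 25% failures in the first 8 weeks, the Protocol's 10% dropout and a cut at the 60th randomization. Accrual of 105 in 36 weeks gives 3.5 to 5 points. No document states that failure pattern, the current SAP assumes 20% dropout, and Protocol 3.1 gives 15 months, so these are not the figures to rely on.
- **Metric.** The estimand summary is the median, which moves less. With 25% failures and a cut at the 60th, the PSL median is 7.1 instead of 7.0 weeks, but the placebo median is 17.8 instead of 16.2. With a cut 12 weeks later both move by 0.1 week or less. This limits the practical effect, but Kaplan-Meier plots are also planned and would show the distortion.
- **Consequence.** After a futility stop with no true effect both arms shift alike, so the comparison hardly changes. This stands; the absolute resolution rates are still too low.

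**Conclusion.** The point holds and should be acted on, but its size is modest. Following the plan as written after a futility stop understates week-24 resolution by about 0.7 to 1.6 points per arm if the stop is 24 weeks after the 60th randomization, and by up to about 3 points with an earlier cut. The same distortion reaches the interim only if it is run on incomplete follow-up. There, mean conditional power moved by at most about 3 points.

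The planned full-follow-up analysis is essentially unaffected. With 20% dropout, a residual understatement of under 1 point remains there under either rule, because dropouts leave the risk set while failures stay.

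Returning to the Protocol's fixed 24 weeks would not cure this, because it has the same defect when follow-up is incomplete.

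Assumptions not in the documents: failures of 10-30% by 24 weeks, the timing of the cut, uniform accrual, 1:1 allocation (2:1 gave similar shifts) and an unstratified test.

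**What to change.** Add to SAP 3.4.1 and 3.7: at the interim, and in any final analysis after early termination, treatment failures are censored at the earlier of 24 weeks and the data cutoff date minus the randomization date. In SAP 3.7, also state the interim data cutoff and the minimum follow-up required of the first 60.

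The cost is a few lines of SAP text and one derived variable. With complete follow-up the rule reduces to 24 weeks, so the planned primary analysis does not change.
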